# 4.2.4 Missed follow up visits

The proportion of missed follow up visits will be reported in the data tables in the study report.

# 4.3 Analysis populations

This feasibility study aims to describe the study population in terms of:

- All-treated population: Any subject randomised and eligible for the study that received at least one part of the intervention
- Protocol-compliant population: Any subject who was eligible, randomised and received the protocol required intervention

#### **5. TRIAL POPULATION**

# 5.1 Screening data

Screening data will be collected and reported in terms of the proportion of eligible patients recruited. This forms the primary outcome of this feasibility study.

# 5.2 Eligibility

Patients are eligible to be included in the study if they meet the following criteria:

#### **Inclusion criteria**

- Patients sustaining OHCA attended by a crew from participating ambulance service
- Resuscitation attempted and shock delivered as per Resuscitation Council UK and JRCALC guidelines

[figure not shown]
#### **Exclusion criteria**

1. Patients known or suspected to be under 18 years old

#### 5.3 Recruitment

Figure 1 Study flow diagram

## 5.4 Withdrawal/follow-up

It will not be possible for patients to withdraw from the intervention since this will have been delivered at a time when they were unconscious. Patients may withdraw from follow up. There are two levels of withdrawal – withdrawal from remote data collection and withdrawal from all data collection (remote and face to face). Both of these will be reported as well as timing of, and reasons for, withdrawal. Numbers of patients lost to follow up will be reported in the study flow chart, broken down for each longer-term follow up assessment in the data tables. Reasons for loss will also be reported.

## 5.5 Baseline patient characteristics

Baseline comparability of the randomised groups will be assessed using the following variables:

- Age (median and range)
- Sex (% male)
- Location of arrest (% private residence/ public place/ other)
- Witnessed vs. unwitnessed event (% witnessed and % bystander/ EMS or other healthcare provider/ unwitnessed)
- Bystander CPR vs. no bystander CPR (of those not EMS-witnessed, % provided BCPR prior to EMS arrival)
- Type of initial rhythm (% in VF/pVT, PEA or asystole)
- Time from call to application of defibrillator (median and range)
- Aetiology of cardiac arrest (% cardiac vs. non-cardiac cause)

#### 6. ANALYSIS

#### 6.1 Outcome definitions

#### **6.1.1** Primary outcome

The proportion (%) of eligible patients who are randomised to receive the intervention will be reported.

#### **6.1.2 Secondary outcomes**

- Treatment adherence rate. This will be assessed in terms of how many patients
  received the allocated first shock energy and, where more than one shock was
  delivered, how many received the correct subsequent shock energies. These will be
  reported as proportions for each treatment arm and overall.
- Data completeness of clinical outcomes below:
  - Neurologically intact survival at 30 days (mRS score)
  - Return Of Organised Rhythm capable of sustaining a pulse (ROOR) 2
     min post shock
  - Resulting rhythm (VF/pVT/PEA/asystole) 2 min post shock
  - Re-arrest rate (re-fibrillation)
  - Survived event (return of spontaneous circulation (ROSC) at hospital handover)
  - Survived to hospital discharge

These will be reported in terms of the proportion of patients for whom each of these outcomes was collected.

- Data completeness of process outcomes below:
  - Quality of CPR (chest compression rate, chest compression depth, chest compression fraction, pre-shock pause, post-shock pause)
  - Number of shocks
  - Advanced airway applied (% advanced airway applied and % supraglottic airway or endotracheal tube)
  - Intravenous medicines administered (% cases where medicines administered and % adrenaline, amiodarone)

Transported to hospital (% transported)

These will be reported in terms of the proportion of patients for whom each of these outcomes was collected.

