#### 3. STUDY METHODS

## 3.1 Trial design

POSED is a single-centre, cluster-randomised multi-arm study. Defibrillators will be randomised to deliver one of three shock strategies:

Group	First shock	Second shock	Subsequent shocks	Strategy
1	120	150	200	Escalating
2	150	200	200	Escalating
3	200	200	200	Fixed

These three shock strategies represent current standard of care in UK Ambulance Services.

This feasibility study aims to recruit 90 patients, ideally 30 in each arm.

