#### 3.2 Randomisation

POSED is a cluster randomised study and the unit of randomisation is the defibrillator. Defibrillators will be allocated to one of the three treatment groups in a 1: 1: 1 ratio using simple randomisation. The randomisation will be stratified by ambulance station and by vehicle type (ambulance/response car/team leader vehicle).

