# **Defibrillation attempts**

	Group A	Group B	Group C	All cases
	(n=)	(n=)	(n=)	(n= )
Number of prehospital shocks				
delivered				

Median (IQR)	Median (Q1:Q3)	Median (Q1:Q3)	Median (Q1:Q3)	Median (Q1:Q3)
Missing - n (%)	n (%)	n (%)	n (%)	n (%)
Total number of shocks delivered				
– n (%)				
1 only	n (%)	n (%)	n (%)	n (%)
1 - 3	n (%)	n (%)	n (%)	n (%)
> 3 shocks	n (%)	n (%)	n (%)	n (%)
Missing	n (%)	n (%)	n (%)	n (%)
Rhythm preceding 1st shock – n				
(%)				
VF	n (%)	n (%)	n (%)	n (%)
pVT	n (%)	n (%)	n (%)	n (%)
Missing	n (%)	n (%)	n (%)	n (%)

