#### **Treatment adherence**

	Group A	Group B	Group C	All cases
	(n= )	(n= )	(n= )	(n= )
1st shock energy				
Delivery of allocated	n (%)	n (%)	n (%)	n (%)
energy				
Missing	n (%)	n (%)	n (%)	n (%)
2 nd shock energy				
Delivery of allocated	n (%)	n (%)	n (%)	n (%)
energy				
Missing	n (%)	n (%)	n (%)	n (%)
3 rd shock energy				
Delivery of allocated	n (%)	n (%)	n (%)	n (%)
energy				
Missing	n (%)	n (%)	n (%)	n (%)

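### The yes/no adherence table cannot show separation between arms at shock 3, and shows it only weakly overall at shock 2; the whole-sequence rule has no row and the shock-count bins overlap

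*SAP*

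**What the plan says.** Section 3.1 of the SAP states "Defibrillators will be randomised to deliver one of three shock strategies". The sequences (first, second, subsequent shocks) are "1 120 150 200 Escalating", "2 150 200 200 Escalating" and "3 200 200 200 Fixed".

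Section 6.1.2 looks at the first shock and, for patients shocked more than once, at the later shocks. The results are "reported as proportions for each treatment arm and overall". Section 4.2.1 promises a table for each of the first three shocks. It also sets a patient-level rule: one departure from the allocated energies within those shocks makes the patient non-compliant.

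The Treatment adherence template in section 7 has, for each of the three shocks, a row beginning "Delivery of allocated" and a Missing row. Its columns are Groups A, B, C and All cases. It has no row for the patient-level rule, no row for the energy given when the allocated one was not, and no count of patients who reached each shock.

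In the Defibrillation attempts template, the item "Total number of shocks delivered" is split into 1 only, 1 - 3, > 3 and Missing.

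**The concern.** Measuring adherence to the allocated treatment is the first secondary objective (section 2.2). For a future trial the useful question is whether crews gave different energies in different arms. A yes/no row answers that only where the arms are allocated different energies. Where they share an energy, a crew following the allocation and a crew ignoring it can both score 'yes'.

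The yes/no format also hides what was given instead. A patient marked non-adherent may have received another arm's energy or something outside all three strategies, and these have different consequences for a main trial.

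The denominators are unclear too. Shocks 2 and 3 apply only to patients who still needed a shock, but the adherence template shows only the arm total, and the shock-count table cannot supply the missing number for shock 3. At stake is a reader taking favourable later-shock percentages as evidence that the strategies were kept apart.

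**Working it through.** **Inputs.** The allocated sequences in section 3.1 are Group 1: 120/150/200, Group 2: 150/200/200, Group 3: 200/200/200. Section 3.2 gives the ratio: "Defibrillators will be allocated to one of the three treatment groups in a 1: 1: 1 ratio using simple randomisation". Section 3.3 gives 30 patients per arm, 3 × 30 = 90. The SAP states no adherence rate or target, so there is no adherence figure to reproduce.

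**Assumptions.** Patient numbers are equal across arms at each shock. Template columns A, B, C are taken as Groups 1, 2, 3.

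**Step 1: where the arms differ.** Shock 1 has three different energies. At shock 2 Group 1 has 150 and Groups 2 and 3 have 200. At shock 3 all have 200.

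**Step 2: adherence if crews ignore the allocation.** Apply one sequence to everyone. Overall adherence at a shock = (number of arms whose allocated energy equals the delivered energy) ÷ 3. Whole-sequence adherence = (number of arms matching at every shock) ÷ 3.

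| Given to everyone | Shock 1 | Shock 2 | Shock 3 | Whole sequence |
|---|---|---|---|---|
| 200/200/200 | 1/3 = 33.3% | 2/3 = 66.7% | 3/3 = 100% | 1/3 = 33.3% |
| 150/200/200 | 1/3 = 33.3% | 2/3 = 66.7% | 3/3 = 100% | 1/3 = 33.3% |
| 120/150/200 | 1/3 = 33.3% | 1/3 = 33.3% | 3/3 = 100% | 1/3 = 33.3% |

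If one of the three sequences is picked at random for each patient, the expected values are 3/9 = 33.3%, 5/9 = 55.6% and 9/9 = 100%, with whole-sequence adherence 3/9 = 33.3%. Because first-shock energies differ in all arms, the whole-sequence figure stays at 33.3% whatever the mix of patients with one, two or three shocks.

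**Step 3: the same by arm.** With 200 given throughout, shocks 1/2/3 read 0/0/100% in Group 1, 0/100/100% in Group 2 and 100/100/100% in Group 3. The by-arm columns expose the problem at shock 1 and, for Group 1, at shock 2. At shock 3 they show nothing.

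**Step 4: later shocks combined.** If adherence to later shocks in section 6.1.2 means shocks 2 and 3 both correct, giving 200/200/200 or 150/200/200 to everyone yields 2/3 = 66.7% overall, and giving 120/150/200 yields 1/3 = 33.3%.

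**Step 5: denominators.** For illustration, suppose 15 of the 30 patients in an arm reach shock 3 and all 15 receive 200. The row reads 15/15 = 100% on those who reached it, or 15/30 = 50% on the arm total. The template does not say which.

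**Step 6: shock-count bins.** Let *a* be the count in 1 only, *b* in 1 - 3 and *c* in > 3. As written, a one-shock patient belongs in both of the first two rows, so *a* + *b* + *c* exceeds the number of patients with data by *a*. Patients with two or three shocks number *b* − *a*, but the split is unknown. The number reaching a third shock is therefore known only to lie between *c* and *c* + (*b* − *a*).

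**The case against.** The SAP reports adherence by arm and by shock, and 'All cases' is one added column. First-shock adherence by arm is already the first item in the text and the first row of the template. A reader might infer that adherence is given only as a pooled figure, that the strategies become identical straight after the first shock, or that crews who disregard the allocation would score well. The documents do not support these readings. Sections 4.2.1 and 6.1.2 and the template give arm-level results. Group 1 still differs at the second shock. Disregarding the allocation gives only 33% on the first-shock and whole-sequence measures, with 0% cells in plain sight. A figure pooled over the first three shocks would lie between 5/9 = 55.6% and 6/9 = 66.7% if every patient had at least three shocks, but the SAP plans no such figure.

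The later rows also have a use. A Group 1 crew that does not reach 200 at shock 3, or a Group 2 crew that does not reach it at shock 2, is rightly counted as non-adherent, so these rows measure whether the escalation was carried out. Finally, the primary outcome is recruitment (section 6.1.1) and the SAP sets no adherence threshold, so no stated decision depends on the 'All cases' adherence cell.

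All of this stands, and it limits the point to how adherence is tabulated and read. It does not give the shock 3 row any power to show separation, supply the missing whole-sequence row, or repair the overlapping bins.

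**Conclusion.** The point holds as a reporting weakness that is cheap to correct. The shock 3 row shows whether 200 was delivered and cannot distinguish the arms, overall or by arm. The overall shock 2 figure is weak evidence of adherence to allocation: it can be 33% to 67% when one sequence is given to everyone, against 33% for both first-shock and whole-sequence adherence. The rule in section 4.2.1 that yields the whole-sequence figure has no place in the template. The shock-count bins are wrong as written, independently of the rest.

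The percentages assume equal patient numbers per arm at each shock. Unequal numbers would move the overall values at shocks 1 and 2 and the whole-sequence value, but not the by-arm pattern or the 100% at shock 3. A reader might go further and conclude that the planned table would conceal wholesale non-adherence. It would not, because the first-shock row by arm would reveal it.

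**What to change.** 1. In the Treatment adherence template, tabulate the delivered energy (120 / 150 / 200 / other / missing) by allocated arm for each of shocks 1 to 3. Show the number of patients who reached that shock and use it as the denominator.
2. Add a row for patient-level adherence under the section 4.2.1 rule. State in section 6.1.2 that first-shock and whole-sequence adherence by arm are the main adherence figures, and that shock 3 is not read as evidence of separation between arms.
3. In the Defibrillation attempts template, change the bins to 1 / 2 / 3 / > 3, keeping the Missing row.

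The cost is a short wording change and a somewhat larger table. Section 3.5 says that the defibrillator downloads record the energy delivered, so no new data are needed. The adherence summary may look less favourable than one that leans on the later shocks.

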## **Secondary Objectives**

- To measure the rate of adherence to the allocated treatment
- Identify the best outcome measures in terms of ease and reliability of recording by reviewing data completeness.
- Explore what affects treatment adherence and data completeness by eliciting the views and experiences of paramedics via focus groups.

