#### 3.3 Sample size

This feasibility study aims to recruit 90 patients, ideally 30 in each arm. It is popularly believed that a sample size should be at least 30, based on the central limit theorem whereby as a population becomes large it achieves an approximately normal distribution. (4) Although these is no statistical proof that 30 is a 'large' number in this context, my sample size of 30 in each treatment arm will be sufficiently large to inform discussion around secondary outcomes whilst allowing for missing data and loss to follow up.

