## 3.7 Timing of outcome assessments

	Cardiac arrest	Hospital	Day 30
Inclusion/exclusion criteria	✓	X	Х
Cardiac arrest data	✓	х	х
Patient identifiers	✓	✓	Х

			THE UNIVER
Adverse event reporting	✓	✓	х
National data opt- out check	,	(	х
Survival checks	√	√	х
Survival status	√	√	√
Hospital stay data	X	√	Х
Notification of enrolment and invitation to take part in follow up	х	√	х
Informed consent	Х	√	х
Neurological outcome (mRS)	x	x	✓

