## **Clinical outcomes**

#### **Electrical outcomes**

	Group A	Group B	Group C	All cases
	(n= )	(n= )	(n= )	(n= )
Rhythm post 1st shock				
ROSC	n (%)	n (%)	n (%)	n (%)
pVT	n (%)	n (%)	n (%)	n (%)
VF	n (%)	n (%)	n (%)	n (%)
PEA	n (%)	n (%)	n (%)	n (%)
Asystole	n (%)	n (%)	n (%)	n (%)
Missing	n (%)	n (%)	n (%)	n (%)

	I			UNIVERSITY OF WARWICK
Rhythm post 2 nd shock				
ROSC	n (%)	n (%)	n (%)	n (%)
pVT	n (%)	n (%)	n (%)	n (%)
VF	n (%)	n (%)	n (%)	n (%)
PEA	n (%)	n (%)	n (%)	n (%)
Asystole	n (%)	n (%)	n (%)	n (%)
Missing	n (%)	n (%)	n (%)	n (%)
Rhythm post 3 rd shock				
ROSC	n (%)	n (%)	n (%)	n (%)
pVT	n (%)	n (%)	n (%)	n (%)
VF	n (%)	n (%)	n (%)	n (%)
PEA	n (%)	n (%)	n (%)	n (%)
Asystole	n (%)	n (%)	n (%)	n (%)
Missing	n (%)	n (%)	n (%)	n (%)
ROOR 2 min post shock - n (%)				
Within 1 shock	n (%)	n (%)	n (%)	n (%)
Missing	n (%)	n (%)	n (%)	n (%)
Within 2 shocks	n (%)	n (%)	n (%)	n (%)
Missing	n (%)	n (%)	n (%)	n (%)
Within 3 shocks	n (%)	n (%)	n (%)	n (%)
Missing	n (%)	n (%)	n (%)	n (%)
Refibrillation rate – n (%)				
Before 2 nd shock	n (%)	n (%)	n (%)	n (%)
Before 3 rd shock	n (%)	n (%)	n (%)	n (%)
Before 4 th shock	n (%)	n (%)	n (%)	n (%)
Missing	n (%)	n (%)	n (%)	n (%)
Time from app. of defibrillator to				
prehospital ROSC – N				
Mean	μ	μ	μ	μ
SD	σ	σ	σ	σ
Median (IQR)	Median (Q1:Q3)	Median (Q1:Q3)	Median (Q1:Q3)	Median (Q1:Q3)
Missing - n (%)	n (%)	n (%)	n (%)	n (%)
Missing - n (%)	n (%)	n (%)	n (%)	n (%)

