# Survival

	Group A	Group B	Group C	All cases
	(n= )	(n= )	(n= )	(n= )
At hospital handover – n (%)				

ROSC	n (%)	n (%)	n (%)	n (%)
CPR ongoing	n (%)	n (%)	n (%)	n (%)
Not conveyed	n (%)	n (%)	n (%)	n (%)
Missing	n (%)	n (%)	n (%)	n (%)
At 30 days- n (%)				
Alive	n (%)	n (%)	n (%)	n (%)
Died in hospital	n (%)	n (%)	n (%)	n (%)
Missing	n (%)	n (%)	n (%)	n (%)
At discharge – n (%)				
Alive	n (%)	n (%)	n (%)	n (%)
Died in hospital	n (%)	n (%)	n (%)	n (%)
Missing	n (%)	n (%)	n (%)	n (%)

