# Neurological outcome at 30 days

	Group A	Group B	Group C	All cases
	(n= )	(n= )	(n= )	(n= )
mRS score at discharge – n (%)				
0	n (%)	n (%)	n (%)	n (%)
1	n (%)	n (%)	n (%)	n (%)
2	n (%)	n (%)	n (%)	n (%)
3	n (%)	n (%)	n (%)	n (%)
4	n (%)	n (%)	n (%)	n (%)
5	n (%)	n (%)	n (%)	n (%)
6	n (%)	n (%)	n (%)	n (%)
Missing	n (%)	n (%)	n (%)	n (%)
mRS score at 30 days – n (%)				
0	n (%)	n (%)	n (%)	n (%)
1	n (%)	n (%)	n (%)	n (%)
2	n (%)	n (%)	n (%)	n (%)
3	n (%)	n (%)	n (%)	n (%)
4	n (%)	n (%)	n (%)	n (%)
5	n (%)	n (%)	n (%)	n (%)
6	n (%)	n (%)	n (%)	n (%)
Missing	n (%)	n (%)	n (%)	n (%)
Neurological outcome - n (%)				
Good (mRS ≤ 3)	n (%)	n (%)	n (%)	n (%)
Death/poor (mRS = 4-6)	n (%)	n (%)	n (%)	n (%)
Missing	n (%)	n (%)	n (%)	n (%)

Sub-group analysis: Neurological outcome of patients with initially shockable rhythm (VF/pVT)

	Group A	Group B	Group C	All cases
	(n=)	(n= )	(n= )	(n= )
mRS score at discharge – n (%)				
0	n (%)	n (%)	n (%)	n (%)
1	n (%)	n (%)	n (%)	n (%)
2	n (%)	n (%)	n (%)	n (%)
3	n (%)	n (%)	n (%)	n (%)
4	n (%)	n (%)	n (%)	n (%)
5	n (%)	n (%)	n (%)	n (%)
6	n (%)	n (%)	n (%)	n (%)
Missing	n (%)	n (%)	n (%)	n (%)
mRS score at 30 days – n (%)				
0	n (%)	n (%)	n (%)	n (%)
1	n (%)	n (%)	n (%)	n (%)
2	n (%)	n (%)	n (%)	n (%)
3	n (%)	n (%)	n (%)	n (%)
4	n (%)	n (%)	n (%)	n (%)
5	n (%)	n (%)	n (%)	n (%)
6	n (%)	n (%)	n (%)	n (%)
Missing	n (%)	n (%)	n (%)	n (%)
Neurological outcome - n (%)				
Good (mRS ≤ 3)	n (%)	n (%)	n (%)	n (%)
Death/poor (mRS = 4-6)	n (%)	n (%)	n (%)	n (%)
Missing	n (%)	n (%)	n (%)	n (%)

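### Data completeness has no stated set of applicable patients, and the section 7 table shells, read literally, overstate it for mRS and understate it for survival and for second- and third-shock outcomes

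*SAP*

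**What the plan says.** The second of the SAP's Secondary Objectives is to "Identify the best outcome measures in terms of ease and reliability of recording by reviewing data completeness". Section 6.1.2 turns this into a secondary outcome for a list of clinical and process measures: "These will be reported in terms of the proportion of patients for whom each of these outcomes was collected". No denominator is named for any of them. Section 6.3 adds that only the proportion missing will be reported. Section 4.2.2 uses the word missing for collection or documentation errors that cannot be put right.

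The only other guide to how completeness will be counted is the set of shells in section 7, where each column is headed by an arm total:

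- **Neurological outcome.** Rows run from mRS 0 to 6 plus missing, and death is grouped with scores 4 to 6. There is a block headed "mRS score at discharge – n" as well as one for 30 days. In the section 3.7 schedule, "Neurological outcome (mRS)" is ticked at Day 30 only.
- **Survival.** The 30-day and discharge blocks each offer alive, "Died in hospital" and missing. The separate out-of-hospital table has rows for death on scene and death in the ambulance.
- **Electrical outcomes.** "Rhythm post 2 nd shock" and its third-shock counterpart list five rhythm or circulation states plus missing.
- **Treatment adherence.** For each of three shocks there are two rows: "Delivery of allocated" energy, and missing.
- **Defibrillation attempts.** The total number of shocks is grouped as one only, one to three, more than three, and missing.

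Section 4.2.1 recognises that some patients will need only one shock. Both 4.2.1 and 6.1.2 limit later-shock adherence to patients who had more than one.

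**The concern.** A completeness figure is informative only if it separates three groups: those in whom the outcome was recorded, those in whom it should have been recorded but was not, and those to whom it did not apply. The text does not make that separation and the shells have no row for the third group. Some known outcomes also have no row of their own.

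The distortion runs in opposite directions for different outcomes. mRS can look well collected because most of its values are deaths, which need no assessment. Survival to discharge can look poorly collected although every patient's status is known. Second- and third-shock rhythm can look poorly collected because some patients never had those shocks. The stated purpose is to compare outcomes on ease and reliability of recording, so opposite errors could change their ranking and steer the main trial towards the wrong measure.

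**Working it through.** **Inputs.** The SAP's only relevant figure is its target: "This feasibility study aims to recruit 90 patients, ideally 30 in each arm". This reproduces as 3 × 30 = 90. The SAP gives no death rate, mRS retrieval rate or distribution of shock counts, so every rate below is an assumption, shown over a range with N = 90.

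**1. mRS at 30 days.** Let D be known deaths by day 30 and k the survivors with an mRS. On the shell, completeness = (D + k)/90. Among survivors it is k/(90 − D). Since k cannot be negative, the shell figure cannot fall below D/90.

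| Deaths D | Survivors | mRS obtained k | Shell figure | Among survivors |
|---|---|---|---|---|
| 63 | 27 | 0 | 63/90 = 70% | 0% |
| 72 | 18 | 0 | 72/90 = 80% | 0% |
| 81 | 9 | 0 | 81/90 = 90% | 0% |
| 72 | 18 | 9 | 81/90 = 90.0% (95% CI 82.1 to 94.6) | 9/18 = 50.0% (29.0 to 71.0) |

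The intervals are Wilson intervals. The shell figure of 90% is reached both with 81 deaths and no survivor assessed and with 72 deaths and half the survivors assessed, so it says little about how readily mRS is obtained.

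**2. Survival.** Let P be deaths before hospital, with every patient's status known. If those deaths go to the missing row because no other fits, completeness = (90 − P)/90.

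- P = 27: 63/90 = 70%
- P = 45: 45/90 = 50%
- P = 63: 27/90 = 30%

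The correct figure is 100% each time. Survival to discharge is on the 6.1.2 completeness list and is directly affected. Thirty-day survival status is not a separate item on that list, but its block has the same gap and also lacks a row for death after discharge. The shells disagree with each other: the same prehospital death is a collected value (mRS 6) in one table and fits only missing in another.

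**3. Second- and third-shock rows.** Let m be the patients who received the shock, all with rhythm recorded. On an arm-total denominator, completeness = m/90.

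- m = 72: 80%
- m = 54: 60%
- m = 36: 40%
- m = 27: 30%

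The figure among those who received the shock is 100% throughout. The same holds for adherence: if 54 patients had a second shock and all 54 received the allocated energy, the arm-total percentage is 54/90 = 60%, whereas the text of 4.2.1 and 6.1.2 gives 54/54 = 100%.

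**4. Shock-count rows.** A single-shock patient fits both the first and second categories. Counted in both, the rows sum to 100% plus the single-shock share: 125% to 145% if that share is 25% to 45% (assumed).

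**5. Discharge mRS.** The shell reports it and the schedule in 3.7 does not collect it. Unless it is collected some other way, the block can hold only deaths and missing values. The good/poor split does not say which of the two mRS assessments it uses.

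**The case against.** A reader might infer that the SAP computes completeness on a wrong denominator. It does not go that far. Section 6.1.2 leaves the denominator undefined, the arm total is a column heading rather than a stated denominator for every row, and section 4.2.2 ties missing to errors that cannot be rectified. A careful analyst could handle inapplicable data sensibly. This stands, and it makes the fault an undefined quantity with misleading shells. But nothing instructs that handling, and the shells provide no other row.

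A reader might also infer that counting deaths as collected mRS is an error. The listed outcome is neurologically intact survival, and for a patient known to have died its value is known. The overall figure is therefore legitimate and should stay; it fails only as evidence of how easily mRS is obtained. Nor can it be said that only survivors can be missing, because the SAP provides for a national data opt-out check, withdrawal and loss to follow-up. The shell shows row 6 separately, so the survivors' pattern can partly be recovered from the counts.

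It would be too strong to say that prehospital deaths have no row anywhere. They appear in the out-of-hospital table, as mRS 6, and, for deaths on scene, as not conveyed at handover. The gap is in the discharge and 30-day survival rows. Likewise, the adherence text already conditions on delivery, and the table has no non-adherent row, so it does not label single-shock patients as non-adherent. The gap there is that the shell does not carry the text's condition.

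Finally, the study tests no hypotheses, and the counts could be re-expressed at reporting. That limits the severity but does not remove the need for a stated rule, since completeness is the declared basis for choosing outcomes.

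**Conclusion.** The point holds as a moderate one. The SAP does not state which patients each completeness figure applies to. Followed literally, its shells put a floor under mRS completeness equal to the death proportion (70% to 90% for 63 to 81 deaths in 90). They cap completeness of survival to discharge at the share not dying before hospital (70% down to 30% for 27 to 63 such deaths), and second- and third-shock rhythm at the share who received that shock (80% down to 30% for 72 to 27 patients). The direction of each distortion follows from the rows; its size rests on rates assumed here. The overlapping shock-count rows and the unscheduled discharge mRS block are smaller errors that need no assumption. The primary outcome, the proportion of eligible patients randomised, is unaffected.

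**What to change.** - In 6.1.2, state the applicable patients for each outcome and define completeness as the proportion of those with the outcome recorded.
- Keep overall mRS completeness and add mRS completeness among patients alive at day 30.
- Use these survival rows: alive; died before hospital; died in hospital; died after discharge (30-day block only); still in hospital (discharge block only); missing.
- Add a shock-not-delivered row for the second and third shocks in the rhythm and adherence tables, including the shockable-rhythm sub-group copy of the rhythm table. Use the patients who received that shock as the denominator.
- Change the one-to-three category to two-to-three.
- Reconcile the discharge mRS block with section 3.7, by scheduling it or removing it (also in the sub-group copy), and state which mRS the good/poor split uses.

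The cost is a short addition to 6.1.2 and edits to the shells, unless discharge mRS is newly scheduled, which would add an assessment; nothing else needs new data. The downside is that mRS completeness in survivors may look less favourable than the overall figure, and with few survivors its interval will be wide (29.0% to 71.0% for 9 of 18).
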